4. OBJECTIVES, ENDPOINTS AND ESTIMANDS

Objectives	Endpoints

Primary
 
• To demonstrate the bioequivalence of binimatinib 45 mg tablet Test formulation in comparison to 3 x 15 mg tablet Reference formulation in healthy participants under fasted conditions.	
• Plasma concentrations of binimatinib and corresponding non-compartmental derived PK parameters [area under the plasma concentration-time curve (AUC) from time of administration to last observed plasma concentration (AUC_{last}), AUC from time of administration to infinity (AUC_{inf}), maximum observed plasma concentration (C_{max}), AUC Test (T)/Reference (R) ratios].

Secondary
 
• To measure secondary PK parameters of binimatinib and PK parameters of the metabolite (AR00426032).• To evaluate the safety and tolerability of binimatinib as a 1 x 45 mg Test tablet in comparison to 3 x 15 mg Reference tablets in healthy participants.	
• Secondary PK parameters of binimatinib: Time to reach C_{max} (T_{max}) and terminal half-life (t_{1/2}, λ_z), residual area (AUC_%Extrap_obs), mean residence time (MRT).• PK parameters of AR00426032: AUC_{last}, AUC_{inf}, C_{max}, T_{max}, t_{1/2}, λ_z, mean residence time (MRT).• Incidence, nature and severity of treatment-emergent adverse events (TEAEs).• TEAEs leading to dose interruption or discontinuation.• Treatment-emergent serious adverse events (treatment-emergent SAEs).• Changes in clinical laboratory parameters, vital signs, electrocardiograms (ECGs), ophthalmologic examinations.

Estimands:

The primary estimands are to demonstrate the bioequivalence of binimatinib 45 mg-tablet in comparison to the currently commercialized 3 x 15 mg tablets in healthy participants under fasted conditions.

Forty (40) healthy participants will be enrolled to obtain a minimum of 36 evaluable healthy participants, who will receive within a crossover design the 2 formulations under fasted conditions.

To demonstrate the bioequivalence between the two formulations, primary PK parameters (AUC_{last}, AUC_{inf} and C_{max}) will be analyzed separately using linear mixed effects model with log-transformed PK parameter as the dependent variable. Point estimates and 90% confidence intervals (CIs) will be provided for the ratio of Test to Reference (45 mg formulation as Test

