9.1. Generalities

Reasons for exclusion:

Before concentration data are communicated by the bioanalytical laboratory, the following rules will lead to exclude a participant from the PK set:

- Any participant who discontinued with study treatment (no administration in the second period),
- Any participant having experienced vomiting or diarrhoea within 4 hours after dosing,
- Any participant having taken prohibited concomitant treatment or medication affecting PK throughout the study,
- Any participant for whom a washout of at least 7 days between each dose was not respected,
- Any participant who did not remain fasted for at least 10 hours before dosing,
- The following deviations will be discussed case by case:
 - Any deviation related to PK sample technical handling or storage,
 - Any participant with insufficient PK samples to support the calculation of primary PK criteria.

In the following cases (exceptions), the decision to exclude a participant from the statistical analysis (i.e. participant kept in the PK set but flagged and only listed, concentrations and parameters will not be used for statistical analysis) could be done after concentration data are communicated by the bioanalytical laboratory:

- 1) Any participant with lack of any measurable concentrations or only very low plasma concentrations for reference formulation (i.e. its AUC is less than 5% of reference formulation geometric mean AUC, calculated without inclusion of data from the outlying participant),
- 2) Any participant with non-zero baseline concentrations $> 5\%$ of C_{max} .

The following rules for **PK parameter calculation** after each administration will be used:

Actual sampling times will be used for deriving PK parameters.

- For plasma concentrations and PK parameters:
 - All BLQ values will be substituted according to the rules described in the following table and by type of analysis:

Substitution value if BLQ occurs:			
Type of analysis	Before T _{max}	After T _{max} & between 2 quantifiable concentrations	After T _{max} & NOT between 2 quantifiable concentrations
PK non-compartmental analysis	0	Missing	Missing
Descriptive statistics	0	0	0
Plotting of individual data	0	Missing	Missing
Listing of individual data	BLQ	BLQ	BLQ

- Some conditions for plasma PK parameters have to be fulfilled:
 - 1) the percentage of the extrapolated AUC (AUC_%Extrap_obs) should not exceed 20% of the AUC_{inf} of each individual profile,

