 - 2) the elimination rate constant should be determined over a time interval equal to at least 2 x t_{1/2},
 - 3) the determination of λ_z should use only those data points judged to describe the terminal log-linear decline resulting in an adjusted coefficient of determination value R² (Rsq_{adj}) ≥ 0.8, and a minimum of 3 data points will be used in calculating λ_z excluding C_{max}.

If these conditions are not fulfilled, the following unreliable PK parameters will be flagged in the listings and will be excluded from the analysis:

- 1) if the time interval used for the determination of the elimination rate constant is inferior to 2 x t_{1/2} and/or not with a minimum of 3 data points and/or if the Rsq_{adj} < 0.8: λ_z, t_{1/2}, AUC_{inf}, CL/F, Vz/F, MRT and MR_{AUC}.
- 2) if AUC_%Extrap_obs > 20%: AUC_{inf}, CL/F, Vz/F, MRT and MR_{AUC}.

No graphic representation will be done if all values are BLQ.

The following rules for **mean plasma concentration calculation** will be used:

- If at least 3 of the values are evaluable (either BLQ values replaced by zero or numeric values): statistics will be calculated with the replaced and numeric values.
- If less than 3 values are evaluable: only the minimum and maximum will be presented and the other statistics will be considered as "Not Applicable" (NA).
- If at least one value is BLQ (replaced by 0), the geometric mean and its CV% will be presented as "Not Calculated" (NC).

For **summary statistics for PK parameters**:

- If at least 3 values are analysable and not missing: statistics will be calculated with the available values.

- If less than 3 values are analysable: only the minimum and maximum of the available numeric values will be presented. All other statistics will not be calculated and will be presented as "Not Determined" (ND).

All BLQ concentrations and missing data will be labelled as such in the concentration data listings.

9.2. *Plasma concentrations and pharmacokinetic parameters*

9.2.1. *Plasma parameters*

Blood samples will be drawn in each treatment period (see section 15.1) at pre-dose and at H0.5, H0.75, H1, H1.25, H1.5, H2, H3, H4, H5, H6, H8, H10, H12, H24, H36, H48 and H72 post-dose of each period.

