Relevant plasma pharmacokinetic (PK) parameters of binimatinib and its metabolite AR00426032 will be calculated by standard non-compartmental methods for the participants with sufficient plasma concentration data (a PK profile with at least 3 quantifiable concentrations). The rules defined in the previous section (9.1) will be used.

The different areas under the concentration-time curve (AUC) will be calculated using the linear-log trapezoidal method: the linear trapezoidal method for increasing or equal concentrations and the logarithmic trapezoidal method for decreasing concentrations.

The following plasma pharmacokinetic parameters will be calculated for binimatinib and AR00426032:

Parameters (unit)	Definition
C_{max} (ng/mL)	Maximum observed plasma concentration
T_{max} (h)	Time to reach maximum observed plasma concentration
T_{last} (h)	Time to reach last observed quantifiable plasma concentration
AUC_{last} (ng/mL.h)	Area under the plasma concentration-time curve from time zero to the last quantifiable plasma concentration
AUC_{inf} (ng/mL.h)	Area under the plasma concentration-time curve from time zero to infinity, calculated as follows: $AUC_{inf} = AUC_{last} + \frac{C_{last}}{\lambda_z},$ where C_{last} is the last observed quantifiable concentration
λ_z (h)	First order terminal elimination rate constant
$t_{1/2}$ (h)	Terminal elimination half-life, calculated as follows: $t_{1/2} = \ln(2)/\lambda_z$
MRT (h)	Mean Residence Time, calculated as follows: $MRT = \frac{AUMC_{inf}}{AUC_{inf}}$ where $AUMC_{inf}$ is the area under the first moment curve from zero to infinity.

The following plasma pharmacokinetic parameters will be calculated only for binimatinib:

Parameters (unit)	Definition
$AUC_{-Extrap_obs}$ (%)	Residual area expressed in percentage

Parameters (unit)	Definition
CL/F (L/h)	Apparent total body clearance, calculated as follows: $CL/F = \text{Dose} / AUC_{inf}$
Vz/F (L)	Apparent volume of distribution, calculated as follows: $Vz/F = CL/F / \lambda_z$
MR _{AUC}	Metabolite-parent ratio based on AUC _{inf} accounting for differences in molecular weights (MW), calculated as follows: $MR_{AUC} = \frac{AUC_{inf\ AR00426032} / MW_{AR00426032}}{AUC_{inf\ binimetinib} / MW_{binimetinib}}$

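### When a λz fit is rejected, SAP 9.1 excludes every λz-dependent parameter except residual area (AUC_%Extrap_obs), so that secondary endpoint's summary may include values from rejected slopes

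*SAP*

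**What the plan says.** SAP Section 9.1 sets three conditions on each profile: a ceiling on extrapolated area, a minimum fitting interval for λz, and a fit-quality requirement (adjusted R² of at least 0.8 on at least three points, Cmax not counted). It then says that where these are not met "the following unreliable PK parameters will be flagged in the listings and will be excluded from the analysis". Two numbered exclusion rules follow, called rule 1 and rule 2 here.

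- **Rule 1 (λz failure).** It applies "if the time interval used for the determination of the elimination rate constant is inferior to" two half-lives, and/or if there are fewer than three points, and/or if adjusted R² is below 0.8. The parameters removed are "λ_z, t_{1/2}, AUC_{inf}, CL/F, Vz/F, MRT and MR_{AUC").
- **Rule 2 (large extrapolation).** It applies "if AUC_%Extrap_obs > 20" percent, and removes AUCinf and the parameters derived from it, but not λz or t1/2.

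Residual area appears in Section 9.1 only as a trigger: "the percentage of the extrapolated AUC (AUC_%Extrap_obs) should not exceed 20% of the AUC_{inf} of each individual profile". SAP Section 9.2.1 lists it among the parameters calculated for binimetinib, defined only in words ("Residual area expressed in percentage"). Protocol Section 4 names it among the secondary PK endpoints of binimetinib: "residual area (AUC_%Extrap_obs), mean residence time (MRT").

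SAP Section 9.2.2 asks for descriptive statistics of the PK parameters by formulation. Section 9.1 computes them on whatever values are available once at least three are analysable and not missing.

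**The concern.** Rule 1 exists to keep quantities that rest on an unreliable terminal slope out of the summaries. Residual area rests on that slope in both numerator and denominator, so leaving it off the list looks like an oversight. A programmer who follows the list literally would keep it in the table.

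At stake is one descriptive table. Residual area tells the reader whether 72 h of sampling captures the exposure, and so how far AUCinf can be trusted. A mean or maximum that includes values from rejected slopes is a less dependable guide to that.

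The error may also have a direction. For a given fitting interval, the span requirement fails when the estimated half-life is long, that is, when the slope is shallow. A shallow slope inflates Clast/λz, so residual areas kept after a span failure would tend to be too high.

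**Working it through.** **Step 1: which parameters use λz.** SAP 9.2.1 gives AUCinf as AUClast plus Clast/λz. Section 9.1 describes residual area as the extrapolated part as a percentage of AUCinf. Hence

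residual area = 100 × (Clast/λz) / (AUClast + Clast/λz).

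| SAP 9.2.1 parameter | Uses λz? | Removed by rule 1? |
|---|---|---|
| Cmax, Tmax, Tlast, AUClast | no | no |
| λz, t1/2 | yes | yes |
| AUCinf, MRT | yes | yes |
| CL/F, Vz/F | yes | yes |
| MR_AUC | yes | yes |
| AUC_%Extrap_obs | yes | **no** |

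Eight of the twelve parameters depend on λz. Rule 1 removes seven of them. Neither document removes the eighth elsewhere.

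**Step 2: when the gap bites.** If no slope is estimated, residual area is missing and there is nothing to exclude. Section 9.1 also requires at least three points in calculating λz, so the under-three-points trigger may yield no value at all. That leaves slopes that were estimated but failed on span or adjusted R².

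**Step 3: size.** The plan gives no figure to reproduce. These inputs are needed:

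- *Half-life (assumed).* Protocol 3.2.5 reports accumulation of about 1.5-fold. Taking this to be on 12-hourly dosing with one-compartment behaviour, 1/(1 − exp(−12k)) = 1.5, so exp(−12k) = 1/3, k = ln 3/12 = 0.0916 per h, and the half-life is ln 2/k = 7.57 h.
- *Tlast (assumed).* One of the late scheduled samples: 24, 36, 48 or 72 h.
- *Correct residual fraction.* f = exp(−k × Tlast), with absorption treated as instantaneous.
- *Wrong slope.* If the fitted slope is c times the true one, the reported fraction is f / (f + c(1 − f)). For c = 1/2 this is 2f/(1 + f), for c = 1/3 it is 3f/(1 + 2f), and for c = 2 it is f/(2 − f).

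| Tlast | Half-lives covered | f | c = 1/2 | c = 1/3 | c = 2 |
|---|---|---|---|---|---|
| 72 h | 9.5 | 1/729 = 0.14% | 2/730 = 0.27% | 3/731 = 0.41% | 1/1457 = 0.07% |
| 48 h | 6.3 | 1/81 = 1.2% | 2/82 = 2.4% | 3/83 = 3.6% | 1/161 = 0.6% |
| 36 h | 4.8 | 1/27 = 3.7% | 2/28 = 7.1% | 3/29 = 10.3% | 1/53 = 1.9% |
| 24 h | 3.2 | 1/9 = 11.1% | 2/10 = 20.0% | 3/11 = 27.3% | 1/17 = 5.9% |

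Only the number of half-lives covered matters, so a longer true half-life acts like an earlier Tlast. For example, 15.1 h with Tlast 72 h gives the 36 h row.

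**Step 4: effect on the table.** With 36 profiles per formulation, each profile whose slope is halved moves the mean by (reported − correct)/36. At 48 h that is (2.44 − 1.23)/36 = 0.03 percentage points, and at 36 h it is (7.14 − 3.70)/36 = 0.10. The maximum can take the full shift from a single profile. How many profiles would fail is not known.

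**The case against.** The strongest defence is that residual area is a coverage diagnostic. Dropping profiles with a poorly defined terminal phase limits the coverage summary to the well-behaved ones and may make coverage look better than it was. This stands in part. It is the right reason to keep residual area under rule 2, where λz itself has not been rejected. It is weaker under rule 1, where the diagnostic is computed from a slope that the SAP has called unreliable. It does mean that exclusion has a small price, which the fix should make visible.

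It is also fair that the SAP nowhere states that these values will be summarised. That follows from a closed list together with the available-values rule. The word analysable is undefined, and the table shells are in a separate document. A careful programmer might drop the values unprompted. A reader can already see in the listings which λz values are flagged.

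Two stronger readings are tempting and not supported:

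- A reader might infer a large distortion, such as a correct 10% reported as 18%. Under the 7.6 h half-life, a correct value near 10% needs Tlast of about 25 h, whereas sampling runs to 72 h. The documents do not show that Tlast would fall that early.
- A reader might treat a different number of observations for residual area and AUCinf as the defect. Rule 2 produces that difference by design, and properly so.

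**Conclusion.** The omission is real and minor. Rule 1 leaves out one of the eight λz-dependent parameters, and no other text removes it. Following the list literally would put residual areas from slopes rejected on span or adjusted R² into the summary of a named secondary endpoint.

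The size cannot be determined from the documents. On the assumptions above, a halved slope roughly doubles a residual area that is small to begin with: a shift of 0.14 to 3.4 percentage points for Tlast between 72 and 36 h, and about 9 points only if Tlast is near 24 h. The half-life is inferred from an approximate accumulation figure, and both the dosing interval behind that figure and the one-compartment shape are assumed.

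A reader might infer that the bioequivalence conclusion is exposed. It is not. Rule 1 already removes AUCinf from a rejected slope, Cmax and AUClast do not use λz, and residual area enters neither the mixed model nor the 0.80 to 1.25 criterion. The change is worth making for internal consistency, and no more than that.

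**What to change.** In SAP Section 9.1, add AUC_%Extrap_obs to the parameters flagged and excluded from summary statistics under the λz-failure rule. Keep the flagged values in the listings. Leave the rule for residual area above 20% unchanged, so that valid high values are still reported.

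Next to the residual-area table, give the number of profiles excluded under the λz-failure rule for each formulation, so that the reader can see how far the coverage summary is restricted to profiles with a reliable terminal slope.

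The cost is one term in a list and one count per formulation. No primary analysis, sample size or listing content changes.

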9.2.2. Plasma pharmacokinetic analysis

Listings with plasma concentrations (including PK blood sampling dates, times and elapsed times) and PK parameters will be provided by formulation group and participant. These listings will be generated for all participants with an available PK profile (complete or incomplete), including those who are excluded from the pharmacokinetic set. Participants excluded will be flagged.

Plasma concentrations and PK parameters of binimetinib and AR00426032 including descriptive statistics will be presented in tables separately for each formulation group.

Individual plasma concentration versus time profiles of binimetinib and AR00426032 will be presented graphically on linear and log/linear coordinates for each participant with all formulations received by the participant on the same graph.

The graph of arithmetic mean \pm SD over time will be provided for plasma concentration of binimetinib and AR00426032 on linear and log/linear coordinates with all formulation groups on the same graph as well as for each formulation group with both analytes on the same graph. Individual plasma concentration-time profiles (spaghetti plots) of binimetinib and AR00426032 will also be presented for each formulation group on linear and log/linear coordinates.

For binimetinib only:

Scatter plots will be generated for the comparison of the C_{max}, AUC_{last} and AUC_{inf} (if applicable) parameters of binimetinib between the formulation groups.

Box whisker plots will be generated for the comparison of C_{max}, AUC_{last} and AUC_{inf} (if applicable) parameters of binimetinib between the formulation groups.

To demonstrate the bioequivalence between the two formulations, primary PK parameters (C_{max}, AUC_{last} and AUC_{inf}) will be analyzed separately using linear mixed effects model with log-transformed PK parameter (variable PARAMCD) as the dependent variable, sequence (TRTSEQPN), period (APERIOD) and formulation (TRTAN) as fixed effects and participant within sequence (USUBJID(TRTSEQPN)) as random effect. Point estimates and 90% CIs will be provided for the ratio of Test to Reference (3 x 15 mg formulation as Reference and 1 x 45 mg formulation as Test). In accordance with EMA and FDA guidelines, bioequivalence will be declared if the 90% CI for the ratio of Test to Reference geometric means is within the range of 80.00% to 125.00% (0.80 to 1.25) for all primary endpoints.

Estimated geometric mean ratios (GMRs) and 90% CIs will also be displayed in a figure.

The following SAS code will be used:

```
proc mixed data=ADPP method=REML;
  by PARAMCD;
```

```

class TRTSEQPN APERIOD TRTAN USUBJID;
model ln(AVAL) = TRTSEQPN APERIOD TRTAN / solution ddfm=kr;
random USUBJID(TRTSEQPN);
lsmeans TRTAN / cl alpha=0.10;
estimate 'Test versus Reference' TRTAN -1 1 / cl alpha=0.10 e;
run;

```

The Wilcoxon signed-rank test will be used to test for the difference in T_{max} of binimatinib between the 2 formulations.

Differences in T_{max} of binimatinib between the 2 formulations will be explored by computing the Hodges-Lehmann shift estimate and the corresponding 90% CI. The difference between the 2 formulations [$di=(xi, yi)$] for each participant and for binimatinib is calculated and sorted, then the average value of the difference of each ordered pair (dj, di) with $i \leq j$ is computed and the median difference is estimated, then the confidence interval for the mean difference is estimated based on the Wilcoxon signed-rank distribution.

10. Pharmacodynamics data

Not applicable.

11. Safety data

The safety analyses will be performed on the safety set.

11.1. Adverse events

Adverse events, including pre-treatment events, will be recorded from the time of consent through until the EOS visit.

A treatment-emergent adverse event (TEAE) is an adverse event that starts or worsens during the on-treatment period. All analyses described in section 11.1 will be based on TEAEs if not otherwise specified.

The following treatment periods will then be considered:

Period	Start date/time	End date/time
Before any treatment	Date/time of inform consent	Date/time of first IMP administration of period 1 - 1 minute
Treatment 1	Date/time of first IMP administration of period 1	Date/time of first IMP administration of period 2 - 1 minute
Treatment 2	Date/time of first IMP administration of period 2	Date of end of study

Adverse events will be summarized by worst grade according to the National Cancer Institute - Common Terminology Criteria for Adverse Events version 5.0 (NCI-CTCAE V5.0 [5]) per participant and coded using MedDRA Version 24.0.

A summary table will present the number and percentage of participants with a TEAE overall and by formulation, including:

- TEAEs;
- TEAEs, grade ≥ 3 ;
- Related TEAEs;
- Related TEAEs, grade ≥ 3 ;
- TEAEs leading to any dose reduction;
- Related TEAEs leading to any dose reduction;
- TEAEs leading to permanent treatment discontinuation;
- Related TEAEs leading to permanent treatment discontinuation;
- Serious TEAEs;
- Related serious TEAEs;
- TEAEs leading to death;
- Related TEAEs leading to death.

Treatment-emergent adverse events will be summarised in tables as follows [overall and by SOC and PT]:

- Number and percentage of participants with at least one TEAE and number of occurrences of a TEAE by formulation and overall,
- By worst NCI-CTCAE grade, with the number and percentage of participants with at least one TEAE and number of occurrences of a TEAE by formulation and overall,
- By causality to study treatment, with the number and percentage of participants with at least one TEAE and number of occurrences of a TEAE by formulation and overall.

If there are only a few treatment-emergent adverse events (≤ 10), only a listing will be generated.

Additionally, AEs related to COVID-19 will be summarised by formulation and overall and listed separately. If there are only a few adverse events related to COVID-19 (≤ 10), only a listing will be generated.

All adverse events reported in the electronic Case Report Form (eCRF) will be listed with the SOC, the PT and the investigator's verbatim. All TEAEs will also be listed with the SOC and the PT. An additional listing will be provided for TEAEs leading to death and other serious and significant TEAEs (SAEs or TEAEs leading to study withdrawal). If more than 10 of these TEAEs are observed, a summary table with the number and percentage of participants with at least one TEAE and number of occurrences of a TEAE by formulation and overall will be provided, as well as three distinct listings (for TEAEs leading to death, TEAEs leading to study withdrawal and SAE).

Note:

- i. The occurrence of an adverse event is defined by the appearance of a new single event, the reappearance of a previously recovered event or the worsening of a continuous event in severity or seriousness (relative to its previous status).
- ii. In the descriptive tables, the number of participants with at least one adverse event/TEAE for a given PT will also correspond to the number of adverse events/TEAEs whatever the number of occurrences during the studied period.
- iii. In case of a change of severity or causality for an event during the same treatment period, the severity will be the highest recorded intensity and the causality will be the highest likelihood recorded.
- iv. SOCs will be sorted by descending order of frequency for the overall, PTs will be sorted by descending order of frequency for the overall within each SOC.

